## 4. OBJECTIVES AND ENDPOINTS

Objectives	Endpoints
Primary	

 
To evaluate the safety of long-term treatment with FF/UMEV/VI combination therapy
 
	
 
Incidence and type of adverse events (AE)/serious adverse events (SAE)
 

Secondary	

 
To evaluate the safety of FF/UMEV/VI combination therapy
 
	
Secondary Endpoints
 
 
Blood pressure/pulse measurements
 
12-lead electrocardiogram (ECG)
 
Clinical laboratory tests (hematology, biochemistry and urinalysis)
 

Other	

 
To evaluate the efficacy of FF/UMEV/VI combination therapy
 
	
Other Endpoints
 
 
Mean change from baseline in trough Forced Expiratory Volume in 1 second (FEV1) at Week 24 and Week 52
 
Mean change from baseline in Asthma Control Questionnaire-7 (ACQ-7) total score at Week 24 and Week 52
 
Mean change from baseline in St. George's Respiratory Questionnaire (SGRQ) total score at Week 24 and Week 52
 
Mean change from baseline in the Asthma Quality of Life Questionnaire (AQLQ) total score at Week 24 and Week 52
 
Unscheduled asthma-related healthcare resource utilization over the 52 weeks of the treatment period
 
Annualized rate of severe asthma exacerbations
 
Annualized rate of moderate/severe asthma exacerbations
 

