## 6.4. Screen Failures

For the purpose of this study, pre-screen failures, screen failures and run-in failures will be defined as follows:

Pre-screen failures: Those subjects that sign the informed consent document but do not have a Visit 1 (screening) procedure.

Screen failures: Those subjects that complete at least one Visit 1 (screening) procedure but do not enter the run-in period. A subject who complete Visit 1 assessments is considered to have entered the run-in period.

Run-in failures: Those subjects that enter the run-in period but do not subsequently enter the treatment period, including those subjects that complete the run-in period and then meet the eligibility criteria but are not assigned to treatment at Visit 2.

The study interactive response technology (IRT) system (RAMOS NG) will be contacted to report pre-screen, screen and run-in failures.

A minimal set of screen failure information is required to ensure transparent reporting of screen failure subjects to meet the Consolidated Standards of Reporting Trials (CONSORT) publishing requirements and to respond to queries from regulatory authorities. Minimal information includes demography, screen failure details, eligibility criteria, and any serious adverse events (SAEs).

Individuals who do not meet the criteria for participation in this study (screen failure) may be rescreened once. Rescreened subjects should be assigned a subject number different from that for the initial screening. Advance written approval to proceed with rescreening a subject must be obtained from the Medical Monitor (see the SRM for contact details).

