### 9.2.1. Time Period and Frequency for Collecting AE and SAE Information

- All SAEs will be collected from the start of study treatment until the follow-up visit at the time points specified in the SoA ([Table 1](#)). Any SAEs assessed as related to study participation (e.g., protocol-mandated procedures, invasive tests, or change in existing therapy) or related to a GSK product will be recorded from the time a subject consents to participate in the study up to and including any follow-up contact.
- All AEs will be collected from the start of treatment until the follow-up visit at the time points specified in the SoA ([Table 1](#)).
- Medical occurrences that begin before the start of study treatment but after obtaining informed consent will be recorded on the Medical History/Current Medical Conditions section of the case report form (CRF) not the AE section.
- All SAEs will be recorded and reported to the sponsor or designee within 24 hours, as indicated in [Appendix 3](#). The investigator will submit any updated SAE data to the sponsor within 24 hours of it being available.
- Investigators are not obligated to actively seek AEs or SAEs in former study participants. However, if the investigator learns of any SAE, including a death, at any time after a participant has been discharged from the study, and he/she considers the event to be reasonably related to the study treatment or study participation, the investigator must promptly notify the sponsor.
- The method of recording, evaluating, and assessing causality of AEs and SAEs and the procedures for completing and transmitting SAE reports are provided in [Appendix 3](#).

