8.2. Adverse Events Analyses

Adverse events analyses including the analysis of adverse events (AEs), Serious (SAEs) and other significant AEs will be based on GSK Core Data Standards. The details of the planned displays are provided in [Appendix 11: List of Data Displays](#).

All AEs will be classified using the standard GSK Medical Dictionary for Regulatory Activities (MedDRA) dictionary, and grouped by SOC and PT, unless otherwise stated. The investigator will evaluate all AEs with respect to seriousness, severity, and causality.

The tabular summary for each type of AE listed below will include the number of participants who reported at least one event, and percentage of participants who reported at least one AE (incidence) for each SOC (where applicable), each PT, and overall. By default, adverse events will be sorted by MedDRA SOCs, in descending order from the SOC with the highest total incidence (i.e., summed across all dose groups) for any adverse event within the class, to the SOC with the lowest total incidence. If the total incidence for any two or more adverse events is equal, the events will be presented in alphabetical order. Only SOCs with observed AE PTs will be presented. Repeat sort order for MedDRA PTs within each SOC.

In principle, all safety analyses will be provided by dose group and total. However, due to Japan regulatory authority requirement, AE analyses by dose at the time of onset of the AE will be prepared in final analyses of this study. Note that dose at the time of onset of the AE will be decided by allocated dose even if a given subject has incorrect study treatment in certain period (but not during all period). If a given subject has incorrect study treatment during all period, then this subject will be analysed according to the treatment which he/she received. In interim analyses, selected tables will be provided. Please refer to Section [11.11.5](#).

Each type of the following will be summarized for both approaches (i.e., by dose group and total, by dose at the time of onset of the AE)

- AE overview during treatment period
- All AEs during treatment period (by SOC and PT; by SOC and PT and maximum severity)
- Drug related AEs during treatment period (by SOC and PT; by SOC and PT and maximum severity)
- Serious AEs during treatment period (by SOC and PT)
- AEs resulting in withdrawal from study (by SOC and PT)

- AEs of Special Interest during treatment period (by SOC and PT)

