11.4. Appendix 4: Study Phases and Treatment Emergent Adverse Events

11.4.1. Study Phases

Assessments and events will be classified according to the time of occurrence relative time of assessment.

Study Phase	Definition
Screening/Run-In period	Visit 1 date \leq Assessment Date/Time $<$ Date of study treatment start date
Treatment period	Study Treatment Start Date \leq Date \leq Date of Visit7/EOT or EW
Follow-up period	Date $>$ Date of Visit7/EOT or EW

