No.	Population	IDSL / Example Shell	Title	Programming Notes	Deliverable [Priority]
12.32.	ITT	AE1	Summary of Adverse Events of Special Interest During Treatment Period by dose at AE (dose: FF/UMEC/V1 200/62.5/25)		SAC [1]
12.33.	ITT	Study Specific	Summary of Adverse Events of Special Interest During Treatment Period per Thousand Person-Year by dose group		IA [1]
12.34.	ITT	AE16	Summary of Serious Adverse Events by System Organ Class and Preferred Term during treatment period (Number of Participants and Occurrences)	FDAAA, EudraCT For studies with few events/participants listing is sufficient: discuss this option with your disclosure representative.	SAC [1]
12.35.	ITT	AE3	Summary of Serious Drug-Related Adverse Events by dose group	PLS	SAC [1]
MACE					
12.36.	ITT	Study Specific	Summary of Major Cardiac Events (MACE) – Narrow Definition		SAC [1]
12.37.	ITT	Study Specific	Summary of Major Cardiac Events (MACE) – Broad Definition		SAC [1]
Laboratory: Chemistry					
12.38.	ITT	LB1	Summary of Chemistry Data		SAC [1]
12.39.	ITT	LB1	Summary of Chemistry Changes from Baseline	ICH E3 Includes Baseline values. Includes pre-specified parameters repeated in conventional units.	SAC [1]
12.40.	ITT	LB3	Summary of Chemistry Shifts from Baseline Relative to Normal Range		SAC [1]

CONFIDENTIAL

207236

Safety: Tables					
No.	Population	IDSL / Example Shell	Title	Programming Notes	Deliverable [Priority]
Laboratory: Hematology					
12.41.	ITT	LB1	Summary of Hematology Data		SAC [1]
12.42.	ITT	LB1	Summary of Hematology Changes from Baseline	ICH E3 Includes baseline values.	SAC [1]
12.43.	ITT	LB3	Summary of Hematology Shifts from Baseline Relative to Normal Range		SAC [1]
Laboratory: Urinalysis					
12.44.	ITT	UR1	Summary of Worst Case Urinalysis Results (Discrete or Character Values) Post-Baseline Relative to Baseline	ICH E3 As above for Chemistry, using dipstick categories. Define change categories according to actual values expected from lab dataset	SAC [1]
Vital Signs					
12.45.	ITT	VS1	Summary of Vital Signs	ICH E3 Includes Baseline values.	SAC [1]
12.46.	ITT	VS1	Summary of Change from Baseline in Vital Signs	ICH E3 Includes Baseline values.	SAC [1]
ECG					
12.47.	ITT	EG2	Summary of ECG Values	IDSL	SAC [1]
12.48.	ITT	EG2	Summary of Change from Baseline in ECG Values	IDSL	SAC [1]
12.49.	ITT	Study Specific	Summary of Categories for QTc (F) Values (Interim)	IDSL	SAC [1]

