11.11.11. ICH Listings (final)

ICH: Listings					
No.	Population	IDS / Example Shell	Title	Programming Notes	Deliverable [Priority]
Subject Disposition					
44.	Screened	ES7	Listing of Reasons for Screen Failure or Run-in Failure	Journal Guidelines	SAC [1]
45.	ITT	ES2	Listing of Reasons for Study Withdrawal	ICH E3 Required for all studies except single dose studies.	SAC [1]
46.	ITT	SD3	Listing of Reasons for Study Treatment Discontinuation	ICH E3	SAC [1]
47.	ITT	TA1	Listing of Planned and Actual Treatments	IDS Note: IDS shell in development.	SAC [1]
Protocol Deviations					
48.	ITT	DV2	Listing of Important Protocol Deviations	ICH E3 Listing also includes analysis population exclusions.	SAC [1]
49.	ITT	IE3	Listing of Participants with Inclusion/Exclusion Criteria Deviations	ICH E3	SAC [1]
Populations Analysed					
50.	Enrolled	SP3	Listing of Participants Excluded from Any Population	ICH E3 e.g., participants screened but not randomized, participants randomized but not treated, participants with deviations leading to exclusion from per protocol population (can be separate listing per population).	SAC [1]

CONFIDENTIAL

207236

ICH: Listings					
No.	Population	IDSL / Example Shell	Title	Programming Notes	Deliverable [Priority]
Demographic and Baseline Characteristics					
51.	ITT	DM2	Listing of Demographic Characteristics	ICH E3	SAC [1]
52.	ITT	DM9	Listing of Race	ICH E3	SAC [1]
Prior and Concomitant Medications					
53.	ITT	CM3	Listing of Asthma Concomitant Medications		SAC [1]
54.	ITT	CM3	Listing of Non-Asthma Concomitant Medications		SAC [1]
55.	ITT	CM6	Relationship between ATC Level 1, Ingredient and Verbatim Text for Non-Asthma Medications		SAC [1]
Exposure and Treatment Compliance					
56.	ITT	EX3	Listing of Exposure Data	ICH E3	SAC [1]
57.	ITT	Study Specific	Listing of Treatment Compliance Data	ICH E3	SAC [1]
Adverse Events					
58.	ITT	AE8	Listing of All Adverse Events	ICH E3	SAC [1]
59.	ITT	AE7	Listing of Subject Numbers for Individual Adverse Events	ICH E3	SAC [1]
60.	ITT	AE2	Listing of Relationship Between Adverse Event System Organ Classes, Preferred Terms, and Verbatim Text	IDSL	SAC [1]
Serious and Other Significant Adverse Events					
61.	ITT	AE8	Listing of Fatal Serious Adverse Events	ICH E3 Fatal and Non-Fatal SAEs are combined into a single listing for ClinPharm studies (i.e., "Listing of Serious Adverse Events").	SAC [1]

CONFIDENTIAL

207236

ICH: Listings					

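### SAEs in the follow-up week are collected and can be listed, but they enter no SAE count; a few SAEs in never-treated participants have no SAE display at all

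*SAP*

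**What the plan says.** **Endpoint and collection.** Protocol section 4 gives the primary endpoint as "Incidence and type of adverse events (AE)/serious adverse events (SAE". Neither that section nor the safety analysis text in 10.3.2 restricts it to time on treatment. Protocol 9.2.1 states: "All SAEs will be collected from the start of study treatment until the follow-up visit at the time points specified in the SoA". SAEs related to study participation or to a sponsor product "will be recorded from the time a subject consents to participate in the study up to and including any follow-up contact". For screen failures, Protocol 6.4 adds: "Minimal information includes demography, screen failure details, eligibility criteria, and any serious adverse events (SAEs".

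**Tables.** SAP 8.2 lists "Serious AEs during treatment period (by SOC and PT" and attaches the same period to the AE overview and the other SAE summaries. In SAP 11.11.6 this covers Tables 12.2, 12.23-12.26 and 12.34, the last titled "Summary of Serious Adverse Events by System Organ Class and Preferred Term during treatment period (Number of Participants and Occurrences". Table 12.35 (serious drug-related AEs) has no period in its title, but the text of 8.2 supplies the treatment period. SAP 11.4.1 ends the treatment period at the "Date of Visit7/EOT or EW" and classes anything later as follow-up.

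**Listings.** The SAE listings (18-20 at interim, 61-63 at final), such as "Listing of Fatal Serious Adverse Events", use the ITT population, which requires at least one dose. Their titles set no period.

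**The concern.** The counting window is narrower than the collection window, and nothing in the protocol's endpoint calls for the narrowing. SAP 2.1 reports no change from the protocol's planned analysis.

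Under Protocol 7.2 the last dose is taken at Visit 7/EOT, or at the early withdrawal visit as appropriate, so the cut falls at about the last dose. An SAE starting the next day is outside every SAE count. Under Protocol 8.1.3 a participant who discontinues treatment leaves the study, so the follow-up week is the only planned safety observation off drug.

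Asthma events are a clear example. Protocol 9.5.4 closes the exacerbation page at Visit 7/EOT or early withdrawal and has later exacerbations recorded as AEs. A serious exacerbation in the follow-up week would then be in neither the SAE tables nor the exacerbation page that feeds the annualized rate.

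At stake is the completeness of SAE incidence in the headline tables and in Table 12.34, which is tagged for FDAAA and EudraCT.

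**Working it through.** The plan states no figure to reproduce. The check sets the collection window beside each display, then sizes the gap.

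**Where a given SAE would appear**

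| SAE | SAE tables | Other tables | Listings |
|---|---|---|---|
| Treated, in treatment period | Yes | Yes | 61-63 |
| Treated, in follow-up (final) | None | 12.6; 12.22 if drug-related; neither marks seriousness | 61-63; 101 if fatal; 93-100 if a listed cardiovascular event |
| Treated, in the week after early withdrawal (interim) | None | None; no follow-up AE table in SAP 11.11.5 | 18-20 possible |
| Never treated, related, non-fatal, non-cardiovascular | None | None | None (SAE listings use ITT) |
| Never treated, related, fatal or cardiovascular | None | None | Final profiles 93-101, on Screened |

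On the interim row, SAP 3.1 takes table data only to Visit 5 or the date of withdrawal. SAP 11.3.2.1 ends the Week 13-24 window at Day 168 for early withdrawals, but that section governs the by-period AE table, which is itself titled as treatment period and does not separate serious events.

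**Size of the follow-up gap**

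Inputs: 110 participants (Protocol 10.1); 52 weeks of treatment and 1 week of follow-up (Protocol 5.1). The SAE rate is not given in the documents, so 2% to 15% per year is an assumption.

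- Share of the all-SAE collection window that the SAE tables cover: 52 / 53 = 98.1%.
- Follow-up person-time, if all 110 reach follow-up: 110 x 7 / 365 = 2.11 person-years.
- Expected uncounted SAEs = rate x 2.11. Chance of at least one = 1 - exp(-rate x 2.11).

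| Assumed rate per year | Expected SAEs | Chance of at least one |
|---|---|---|
| 2% | 0.04 | 4% |
| 5% | 0.11 | 10% |
| 10% | 0.21 | 19% |
| 15% | 0.32 | 27% |

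One participant is 1 / 110 = 0.9 percentage points of incidence, and only if that participant has no SAE already counted.

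**Interim.** With the protocol's 10% drop-out over the whole 52 weeks, at most about 11 participants would have left by Week 24. Their follow-up time is 11 x 7 / 365 = 0.21 person-years. At the same assumed rates that is about 0.004 to 0.03 SAEs.

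**The case against.** **Follow-up SAEs are not hidden.** A reader might infer that the ITT limit on the listings also removes follow-up SAEs. It does not. Everyone in follow-up has been dosed and is in ITT, the listing titles set no period, and SAP 11.7.1 says all available data from withdrawn participants will be listed. Such an event can appear as serious in Listing 61 or 62, and in 63. This stands: the gap is in the counts.

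**The interim package may still show the event.** SAP 3.1 applies its data limit to tables and figures, and the cut-off date is Visit 5 of the last enrolled participant. A post-withdrawal SAE before that date may be in Listings 18-20. This also stands, so the point is limited to interim tables.

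**ITT is the protocol's own safety population.** Protocol 10.2 and 10.3.2 say so, so using it is not a departure by the SAP. An SAE before dosing in someone never treated does not belong in treatment incidence, and before first dose only related SAEs are collected. All of this stands. What remains is that Protocol 6.4 requires SAE information for screen failures and no SAE display carries it. Profiles 93-101 fill part of the gap, at the final analysis only.

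**On-treatment counting is a legitimate, labelled choice.** Follow-up events are tabulated separately in 12.6, and participants may take any prescribed medication after Visit 7/EOT. That is a good reason to keep the on-treatment tables, but not to leave serious follow-up events uncounted as serious. Table 12.22 already pools both periods for drug-related AEs.

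**Disclosure.** It is tempting to say that Table 12.34 breaches disclosure rules. The documents do not state what period those rules require, so that cannot be concluded here.

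**Conclusion.** The AE overview and all SAE tables stop at Visit 7/EOT or early withdrawal, while the protocol collects all SAEs to the follow-up contact and sets no on-treatment limit on the primary endpoint. A follow-up SAE in a treated participant can be listed but enters no SAE count. At interim, one arising after an early withdrawal is in no table, though it may be listed. Separately, a related, non-fatal, non-cardiovascular SAE in a screen or run-in failure has no SAE display.

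The expected size is modest. The estimate above rests on an assumed SAE rate, on all 110 participants reaching follow-up, and on the same constant rate in follow-up as on treatment. If serious events cluster after participants stop because of an event, the true figure would be higher; the documents give no basis for saying by how much. The case for acting is that the data are already collected and the endpoint is primary. The documents do not support the wider claim that follow-up SAEs are missing from the report.

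**What to change.** - **Final tables.** Keep the on-treatment SAE tables. Add SAE and death counts from first dose to the follow-up contact: a row in Table 12.2 and treatment-plus-follow-up versions of 12.23 and 12.34. At minimum, add a serious row to Table 12.6. Doing this by dose group avoids having to assign a dose to events after the last dose. Table 12.26 can stay as it is, since its denominator is treatment exposure.
- **Interim tables.** Do the same for Tables 2.2, 2.11 and 2.16 for participants who withdrew before Week 24.
- **Never-treated participants.** Add one listing of SAEs in non-ITT participants, on All Subjects so that it also covers those who consent but have no screening procedure. Do not add them to ITT incidence.
- **Title.** State the period in the title of Table 12.35.

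The cost is SAP wording and extra programming, with no new data collection. The reported SAE count may be slightly higher.
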